### **Handling of participants after definitive intervention discontinuation**

Participants will be followed-up according to the study procedures specified in this protocol up to the scheduled date of study completion, or up to recovery or stabilization of any AE to be followed-up as specified in this protocol, whichever comes last.

Participants who discontinue the study intervention prematurely (prior to completing the 24-week treatment period) will perform, as soon as possible, the early termination visit with all assessments normally planned for the EOT Visit (Visit 6), to assure a complete clinical assessment in close temporal proximity to the premature termination of study treatment is available.

In addition, and to allow assessment of participant outcomes over the stipulated study period, patients will be asked and encouraged to complete all remaining study treatment visits, and participate in all assessments according to the visit schedule with a  $\pm 3$  day window. Under exceptional circumstances when a participant cannot come to the site for a scheduled visit, a phone contact can be made. During the phone contact, at least information about AEs, concomitant medication and status of PN should be collected.

All cases of definitive intervention discontinuation must be recorded by the Investigator in the appropriate pages of the eCRF when considered as confirmed.

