**Employment status**

1. Have you been working since your last assessment?

- Yes – I am working full time ( $\geq 4$  days/week)
- Yes – I am working part time ( $< 4$  days/week)
- No – I am not working (unemployed, retired)

For those working (full time or part time):

2. How many days have you missed from work because of your Prurigo Nodularis since the day of your last assessment, including today?

*Please do not include time you missed from work for taking part in this research.*

Specify: \_\_\_\_ Days

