**NOTES:**

Please make sure the instructions are read to the patient BEFORE they start the questionnaire.

Assessment periods (i.e., time interval from the date of last assessment through the current date) must be continuous. Leave no gaps. Cumulatively, these periods must cover the entire study duration.

Avoid duplicate reporting. If the patient missed school/work because of his/her PN on the day of assessment, this day should be recorded only once.

**Record only days on which patient's PN prevented him/her to go to school/work. Otherwise, do not record the days on which the patient missed school/work only to participate in study visits.**

---

Print Name (First/Last) of Investigator Completing Assessment      Signature      Date

R668-XXX Missed School/work Days Version 2.0; date

Page 1 of 1

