### Missed school/work days

Participants who are employed or enrolled in school will be asked to report the number of sick leave/missed school days since the last study assessment.

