**Table 10 - Time window for eDiary efficacy variables**

Time	Target day	Day range for calculating weekly score
Baseline (Week 0)	1	-7- <1
Week 1	8	1-11
Week 2	15	12-18
Week 3	22	19-25
Week 4	29	26-32
Week 5	36	33-39
Week 6	43	40-46
Week 7	50	47-53
Week 8	57	54-60
Week 9	64	61-67
Week 10	71	68-74
Week 11	78	75-81

Time	Target day	Day range for calculating weekly score
Week 12	85	82-88
Week 13	92	89-95
Week 14	99	96-102
Week 15	106	103-109
Week 16	113	110-116
Week 17	120	117-123
Week 18	127	124-130
Week 19	134	131-137
Week 20	141	138-144
Week 21	148	145-151
Week 22	155	152-158
Week 23	162	159-165
Week 24	169	166-172
Week 25	176	173-179
Week 26	183	180-186
Week 27	190	187-193
Week 28	197	194-200
Week 29	204	201-207
Week 30	211	208-214
Week 31	218	215-221
Week 32	225	222-228
Week 33	232	229-235
Week 34	239	236-242
Week 35	246	243-249
Week 36	253	250-256

For other efficacy variables, all available values of scheduled measurements will be assigned to the appropriate visit window according to [Table 11](#). In the event of multiple measurements of the same test in the same window, the one closest to the targeted visit date will be used for the by-visit summary. If they are at the same number of days away from the target day, the latest one will be used.

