**Table 11 - Time window for efficacy variables**

Visit	Target Day	Time windows for				
		DLQI, IGA PN-A/PN-S	HADS, EQ-5D-5L, Missed school/work days	PGIS	PGIC	PAS
Visit 1 (Week -4 to -2)	<1			<-14		<-14
Visit 2 (Week 0)	1	1-	1-	-14-1-		-14-1-
Visit 3 (Week 4)	29	1+-42		1+-42	1+-42	1+-42
Visit 4 (Week 8)	57	43-70		43-70	43-70	43-70
Visit 5 (Week 12)	85	71-126	1+-126	71-126	71-126	71-126
Visit 6 (Week 24)	169	127-210	127-210	>126	>126	127-210
Visit 7 (Week 36)	253	>210	>210			>210

1-: up to randomization and before 1st dose date/time; 1+: after randomization or 1st dose date/time

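### The closest-to-target window rule leaves days out of the by-visit summary of missed school/work days when an early-termination form and a scheduled form share a window

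*SAP*

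**What the plan says.** SAP 5.4 (Appendix 4, analysis windows, text after Table 10) states that for efficacy variables other than the daily diary scores "all available values of scheduled measurements will be assigned to the appropriate visit window". If a window holds several records of the same test, "the one closest to the targeted visit date will be used for the by-visit summary"; a tie goes to the later record.

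Table 11 has one column headed "HADS, EQ-5D-5L, Missed school/work days". Its windows are: Visit 5, target Day 85, from after randomization or first dose to Day 126; Visit 6, target Day 169, Days 127-210; Visit 7, after Day 210. No exception is made for missed days.

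The post-baseline form in Protocol 10.7.11 asks: "How many days have you missed from work because of your Prurigo Nodularis since the day of your last assessment, including today". The school item has the same recall period, and SAP 4.5.1 says that participants "report the number of sick leave/missed school days since the last study assessment". The notes to the form ask for continuous periods without gaps and add: "Cumulatively, these periods must cover the entire study duration".

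The schedule of activities (Protocol 1.3) places this form at Week 12, at the end-of-treatment visit (Week 24) and at the end of study. Footnote b and Protocol 7.1.1 require a participant who stops treatment early to undergo the end-of-treatment assessments at that time. Such participants are also asked to complete all remaining visits.

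SAP 4.5.1 lists missed school/work days through Week 24 as exploratory. SAP 4.5.2 plans the number and percentage of participants with events in observed cases, and a Kaplan-Meier analysis of time to first event. It does not say which forms feed these results or how counts from several forms are combined.

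**The concern.** HADS and EQ-5D-5L describe the participant at, or shortly before, the visit, so keeping the record nearest the target day is reasonable. Missed days are a running count cut into intervals. Each form's recall starts where the previous form ended ("since the day of your last assessment, including today"), so no later form can recover what a discarded form recorded.

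The schedule creates the conflict by design. A participant who stops treatment and stays in follow-up produces one more form than the windows allow for, and the rule then keeps a single form per window. The result is an incomplete by-visit count for that participant. If the same selected records also fed the analyses in SAP 4.5.2, a participant whose missed days were all on the discarded form would count as event-free. One with further missed days on a retained form would have a later first event.

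**Working it through.** The plan states no figure for this point, so there is none to reproduce. The check applies the Table 11 rule to one participant.

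**Inputs.** Baseline form on Day 1; scheduled forms on Days 85 and 169 (Table 11 targets); early-termination form on Day t. Windows: after Day 1 to Day 126, and Days 127-210. Each form covers the days since the previous form. Total to cover: 169 - 1 = 168 days.

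**Which form is discarded, and what it covers.**
- t from 2 to 84: the forms on Day t and Day 85 share the first window. Day 85 is on target and is kept. Days lost = t - 1.
- t from 86 to 126: same window, Day 85 is kept. Days lost = t - 85.
- t from 127 to 168: the forms on Day t and Day 169 share the second window, and Day 169 is kept. Days lost = t - 85.

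| Early-termination day | Days lost | Share of 168 |
|---|---|---|
| 29 | 29 - 1 = 28 | 17% |
| 60 | 60 - 1 = 59 | 35% |
| 84 | 84 - 1 = 83 | 49% |
| 100 | 100 - 85 = 15 | 9% |
| 127 | 127 - 85 = 42 | 25% |
| 150 | 150 - 85 = 65 | 39% |
| 168 | 168 - 85 = 83 | 49% |

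For the stop on Day 60, the three forms cover 59, 25 and 84 days (sum 168). The rule keeps 25 + 84 = 109.

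Every early-termination day from 2 to 168, other than Day 85 itself, shares a window with a scheduled form. That is 166 of 166 days, with between 1 and 83 days lost.

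**Visits off target.** With the Week 12 visit on Day 82 or 88 and the Week 24 visit on Day 166 or 172 (the ±3-day window), every early-termination day tested, up to Day 165, still loses coverage; the maximum is 81 to 83 days. Occasionally the scheduled form is the one dropped. With early termination on Day 84 and the visit on Day 88, the distances from target are 1 and 3, so the early form is kept and 88 - 84 = 4 days are lost.

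**If the early form is not a scheduled measurement.** It then never enters a window. With the stop on Day 60, the Day 85 form still starts its recall at Day 60, so the same 59 days are missing.

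**With all forms used.** Coverage is 168 of 168 days for any t.

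**The case against.** The strongest reply is that the rule is written for the by-visit summary, while this endpoint is cumulative. SAP 4.5.2 takes it out of the standard methods and analyses it in observed cases, which is compatible with using every form collected. This stands. A reader might infer that the days are lost whatever statistic is reported, but the documents do not say that. For the results through Week 24 they leave the record set open.

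A reader might also turn the table into an average. Over the 166 possible days the mean loss is 2 × (1 + ... + 83) / 166 = 42 days, and 42/168 = 25%. That is not a bias in a planned result. It assumes stopping days spread evenly and attendance at both visits, neither of which the documents support. It also measures calendar coverage, whereas SAP 4.5.2 plans no total or rate. For a yes/no outcome, status changes only if all of a participant's missed days are on the discarded form.

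A third inference is that the loss differs between arms because it follows treatment discontinuation. It could, but nothing in the documents gives discontinuation by arm or shows an imbalance.

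The affected group is also narrow: employed or studying, stopping treatment early, completing the early form, returning for the next one, and having missed days on the form that is dropped. The protocol expects permanent discontinuation to be rare. The 15% dropout in the sample size section does not count this group, since someone who leaves the study supplies no second form.

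What the reply does not remove is that Table 11 names this variable and gives the only record-selection rule the SAP has for it. Followed as written, that rule produces an incomplete by-visit count.

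**Conclusion.** The point holds for the by-visit summary. The closest-to-target rule is wrong for an interval count and conflicts with the form's own continuity requirement. For a participant with both an early-termination form and the scheduled forms on Days 85 and 169, it omits 1 to 83 of 168 days, for example 59 for a stop on Day 60 and 65 for a stop on Day 150. These are days of coverage; how many missed days they contain is unknown.

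For the number and percentage with events and the time to first event through Week 24, the effect is conditional on those analyses using window-selected records, which the SAP neither states nor excludes.

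The number of participants affected cannot be derived from the documents and is probably small. The endpoint is exploratory and in neither testing hierarchy in SAP 4.6, so no confirmatory result is touched. This is a low-priority correction, worth making because it is cheap.

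**What to change.** In SAP 5.4, exempt missed school/work days from the closest-value rule. State that every post-baseline form up to the Week 24 assessment is used, including the early-termination form, and that where counts are summarised by window the counts of all forms in that window are added.

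In SAP 4.5.2, state that any of these forms can supply the event, and that time to first event is taken from the first form reporting a missed day. This keeps the planned analyses as they are; no new rate variable is needed.

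The cost is about one sentence in each place and a small programming change before the primary database lock. It needs no new data and no change to trial conduct or the testing hierarchy.

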**Table 11 - Time window for efficacy variables**

Visit	Target Day	Time windows for				
		DLQI, IGA PN-A/PN-S	HADS, EQ-5D-5L, Missed school/work days	PGIS	PGIC	PAS
Visit 1 (Week -4 to -2)	<1			<-14		<-14
Visit 2 (Week 0)	1	1-	1-	-14-1-		-14-1-
Visit 3 (Week 4)	29	1+-42		1+-42	1+-42	1+-42
Visit 4 (Week 8)	57	43-70		43-70	43-70	43-70
Visit 5 (Week 12)	85	71-126	1+-126	71-126	71-126	71-126
Visit 6 (Week 24)	169	127-210	127-210	>126	>126	127-210
Visit 7 (Week 36)	253	>210	>210			>210

1-: up to randomization and before 1st dose date/time; 1+: after randomization or 1st dose date/time

### ***Safety assessment***

For the safety assessment, the reference date for the derivation of relative days of events or findings will be the date of first IMP administration. Selected safety variables will be summarized by the analysis window define in [Table 12](#) for the by visit descriptive analysis. All available values from central lab will be assigned to the appropriate visit window. In the event of multiple measurements of the same test in the same window, the one closest to the targeted visit date will be used for the by-visit summary. If they are at the same number of days away from the target day, the latest one will be used. For procedures planned on Visit 2, if it is done on the same date as the first IMP injection but the performance time is missing, it will belong to Visit 2 time window.

**Table 12 - Time window for safety endpoints**

Visit	Target Day	Time windows for							
		Vital signs	Hematology, biochemistry	Urinalysis	CD4 T cell count and HIV test	Serum Pregnancy test	Urine Pregnancy test	Physical examination	ECG
Visit 1 (Week -4 to -2)	<1	<-14	<-14	<-14	1-	<-14		<-14	1-
Visit 2 (Week 0)	1	-14-1-	-14-1-	-14-1-			-14-1-	-14-1-	
Visit 3 (Week 4)	29	1 + -42	1 + -42	1 + -42			1 + -42		
Visit 4 (Week 8)	57	43-70	43-70	43-70			43-70		
Visit 5 (Week 12)	85	71-126	71-126	71-126			71-126		
Visit 6 (Week 24)	169	127-210	127-210	>126	1 +		127-210	1 + -210	1 +
Visit 7 (Week 36)	253	>210	>210				>210	>210	

1-: up to 1st dose date/time; 1+: after 1st dose date/time;

### ***Pharmacokinetics/pharmacodynamics assessment***

For the pharmacokinetics/pharmacodynamics variables summary, the reference date for the derivation of relative days of measurements will be the date of first IMP administration if the participant is treated with study treatment, or the randomization date if the participant is not treated. Pharmacokinetics /pharmacodynamics variables will be summarized by the analysis window defined in [Table 13](#) for the by visit descriptive analyses. All available values of measurements will be assigned to the appropriate visit window. In the event of multiple measurements of the same test in the same window, the one closest to the targeted visit date will be used for the by-visit summary. If they are at the same distance to the target day, the latest one will be used. For procedures planned on Visit 2, if it is done on the same date as the first IMP injection but the performance time is missing, it will belong to Visit 2 time window.

**Table 13 - Time window for pharmacokinetics/pharmacodynamics variables**

Visit	Target day	Time windows for		
		Serum dupilumab concentration	Anti-drug antibodies	Total IgE
Visit 1 (Week -4)	<1			
Visit 2 (Week 0)	1	1-	1-	1-
Visit 3 (Week 4)	29	1+-42		1+-42
Visit 4 (Week 8)	57	43-70		43-70
Visit 5 (Week 12)	85	71-126	1+-126	71-126
Visit 6 (Week 24)	169	127-210	127-210	127-210
Visit 7(Week 36)	253	>210	>210	>210

1-: up to 1st dose date/time or randomization if participant is not treated; 1+: after 1st dose date/time or randomization date if participant is not treated;

### **Unscheduled visits**

Unscheduled visit measurements of laboratory data, vital signs, and ECG will be used for computation of baseline, the last on-treatment value, analysis according to PCSAs, and the shift summaries for safety. They will also be included in the by-visit summaries if they are re-allocated to scheduled visits.

## 5.5 APPENDIX 5 SAMPLE SAS CODE

The multiple imputation and analysis model for the primary analysis of change from baseline in WI-NRS at Week 12 will be built with the following sample SAS code.

1. 40 datasets with a monotone missing pattern will be obtained, induced by Markov Chain Monte Carlo (MCMC) method on participants who have not taken the prohibited medications and/or rescue medications or have discontinued study treatment due to lack of efficacy prior to Week 12.

```
proc mi data=dat_etd seed=16460 n impute=40 out=dat_mc;  
  mcmc impute=monotone;  
  var atopicyн stableyn region antidblyn trt01p winrsbl chg1winrs ...  
    chg24winrs;  
  run;
```

2. For each of the imputed dataset with monotone missing pattern in step 1, the remaining missing data will be imputed using the regression method for the monotone pattern with adjustment for covariates including intervention groups, documented history of atopy (atopic or non-atopic), stable use of TCS/TCI (yes or no), region, baseline anti-depressant use (yes or no), and baseline value of the response variable.

```
proc mi data=dat_mc n impute=1 seed=16461 out=dat_mi;  
  by _imputation_;  
  class atopicyн stableyn region antidblyn trt01p;  
  monotone method=reg;  
  var atopicyн stableyn region antidblyn trt01p winrsbl chg1winrs ...  
    chg24winrs;  
  run;
```

3. Each of the 40 imputed datasets will be merged with the one dataset imputed by WOCF approach, and then be analyzed using the main statistical model. These 40 imputed datasets will be saved.

```
%macro w1;  
  %do i=1%to 40;  
    data wocf&i.;  
    set wocf;  
    _imputation_=&i.;  
    run;  
  %end;  
  data wocf_all;  
  set %do j=1 %to 40; wocf&j. %end;;  
  run;  
%mend w1;
```

```
%w1

data dat_imp;
  set dat_mi  wocf_all;
Run;

proc sort data=dat_imp;
  by _imputation_;
run;

proc glm data= dat_imp;
  by _imputation_;
  class atopicyn stableyn region antidblyn trt01p;
  model chg24winrs = atopicyn stableyn region antidblyn
    trt01p winrsbl;
  lsmeans trt01p / stderr;
  estimate 'Diff Dupilumab vs Placebo' trt01p -1 1;
  ods output LSMeans=implsmeans Estimates=implsmeandiff;
run;
```

4. Applying Rubin's rule to combine analysis results (point estimates and standard errors) from 40 imputations using PROC MIANALYZE for the LS means and difference in LS means between dupilumab and placebo. Sample code:

```
proc sort data=implsMeans; by trt01pn _imputation_; run;

proc mianalyze data= implsmeans;
  by trt01pn;
  modeleffects lsmean;
  stderr stderr;
  ods output ParameterEstimates=lsmeans;
run;

proc mianalyze data=implsmeandiff;
  modeleffects estimate;
  stderr stderr;
  ods output ParameterEstimates=lsmeandiff;
run;
```

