### **5.3 APPENDIX 3 DEMOGRAPHICS AND BASELINE CHARACTERISTICS, PRIOR OR CONCOMITANT MEDICATIONS/PROCEDURES**

#### ***Demographics, baseline characteristics, medical surgical history***

The following demographics and baseline characteristics, medical and surgical history and disease characteristics at baseline will be summarized using descriptive statistics in the randomized population.

Demographic variables are

- Age in years (quantitative and qualitative variable: 18-<40, 40-<65, 65-<75, and  $\geq 75$  years),
- Gender (Male, Female),
- Race (White, Black or African American, Asian, American Indian or Alaska Native, Native Hawaiian or other Pacific Island, unknown),
- Ethnicity (Hispanic or Latino, Not Hispanic or Latino, Unknown)
- Region (Asia: Taiwan, South Korea; East Europe: Hungary; Latin America: Chile; Western Countries: USA, Canada, France, Italy, Portugal, Spain, and UK)
- Territory (North America: USA, Canada; European Union: France, Italy, Portugal, Spain, Hungary, and UK; Rest of World: Taiwan, South Korea, Chile)
- Weight in kg (quantitative and qualitative variable: (<60,  $\geq 60$ - <90,  $\geq 90$  kg)
- BMI in kg/m^2 (quantitative and qualitative variable: <25,  $\geq 25$ - <30,  $\geq 30$  kg/m^2)

Baseline safety and efficacy parameters (apart from those listed above) will be presented along with the safety and efficacy summaries.

Medical (or surgical) history includes all the relevant medical (or surgical) history during the lifetime of the participant.

This information will be coded using the version of MedDRA currently in effect at Sanofi at the time of database lock.

Comorbidity will be summarized separately. The following comorbid diseases will be summarized from electronic case report form (eCRF) pages which were filled in by investigators based on participant reporting.

- Prurigo nodularis (Yes, Ongoing condition)
- Atopic dermatitis (Yes, Ongoing condition)
- Allergic rhinitis history (Yes, Ongoing condition)
- Allergic rhinoconjunctivitis (Yes, Ongoing condition)
- Asthma history (Yes, Ongoing condition)

- Food allergy history (Yes, Ongoing condition)
- Eosinophilic esophagitis history (Yes, Ongoing condition)

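### SAP Appendix 5 presents its code for the Week 12 WI-NRS change, with a Week 12 event cut-off, but its ANCOVA step models the Week 24 change

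*SAP*

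**What the plan says.** SAP Section 5.5 (Appendix 5) opens by stating what its code serves: "for the primary analysis of change from baseline in WI-NRS at Week 12 will be built with the following sample SAS code". The text of step 1 defines who enters the MCMC imputation and leaves out those with prohibited or "rescue medications or have discontinued study treatment due to lack of efficacy prior to Week 12". After the merge with the worst-observation-carried-forward (WOCF) data, step 3 fits PROC GLM with "model chg24winrs = atopicyn stableyn region antidblyn" plus treatment and baseline WI-NRS. The dependent variable is the change at Week 24.

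The governing rules stand elsewhere in the SAP:

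- Table 3, in its row for the Week 24 change, removes from the MI set anyone with prohibited or rescue medication, or a lack-of-efficacy discontinuation, before Week 24. Footnote a carries the same strategy to endpoints at other weeks.
- Section 4.4.2 ties the medication exclusion to the timepoint of whichever endpoint is being analysed. It refers the reader to Section 5.5 for the code of both imputation and analysis.
- Section 4.6 places the percent change in WI-NRS at Week 24 in both testing hierarchies. The Week 12 change is in neither.

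On a lesser matter, Section 5.3 defines four regions: "Region (Asia: Taiwan, South Korea; East Europe: Hungary; Latin America: Chile; Western Countries: USA, Canada, France, Italy, Portugal, Spain, and UK". The step 1 call uses "mcmc impute=monotone" with region in its variable list and no CLASS statement. In step 2 and in PROC GLM, the CLASS statement includes "stableyn region antidblyn trt01p".

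**The concern.** A programmer who opens Section 5.5 finds a Week 12 heading, a Week 12 exclusion rule and a Week 24 outcome in one block. Nothing in the block shows whether the outcome should move to Week 12 or the heading and cut-off should move to Week 24. The appendix is the only place that prints the sequence of MCMC, monotone regression and merge with the WOCF data, so it will be adapted for every continuous endpoint.

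Two things are at stake. A Week 12 analysis that keeps the printed outcome would report the Week 24 effect under a Week 12 label. A Week 24 analysis that keeps the printed cut-off would treat participants rescued between Weeks 12 and 24 differently from what Table 3 requires.

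**Working it through.** No figure in the plan underlies this point, so there is none to reproduce. The check sets the code against the rules.

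| Element | Printed block | Week 12 endpoint requires | Week 24 endpoint requires |
|---|---|---|---|
| Declared endpoint | Week 12 | Week 12 | Week 24 |
| Event cut-off for the MI set | Week 12 | Week 12 | Week 24 |
| Outcome in PROC GLM | `chg24winrs` | `chg12winrs` | Week 24 change |

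Read as a Week 12 block, one element is wrong: the outcome. Read as a Week 24 block, two are wrong: the declared endpoint and the cut-off.

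An example shows what the second reading does. Take a participant rescued at Week 18. Under Table 3 for Week 24, this participant leaves the MI set, later values are set to missing, and the worst post-baseline value up to the rescue is used. Under the printed step 1 the event is not before Week 12, so the participant stays in the MI set and the missing Week 24 value is drawn by MI. For a lack-of-efficacy discontinuation at Week 18, observed values are kept either way. Only a missing Week 24 value is treated differently: WOCF under Table 3, MI under the printed cut-off.

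To gauge size, the Appendix 5 sequence was simulated: multivariate-normal MCMC to a monotone pattern, monotone regression, WOCF merge, ANCOVA and Rubin's rule. Each scenario used 150 participants, 25 trials and 8 imputations. Every input on effect, spread and events is an assumption. These include mean Week 24 changes of -5.0 on dupilumab and -2.7 on placebo, and base rescue rates to Week 12 of 5% and 12%, raised for poor responders and lowered for others. Late events were rescue only. Base late-rescue rates (dupilumab/placebo) were 0/0, 3%/8% and 5%/20%. A fourth scenario repeated 3%/8% with a strong non-ordinal region effect of ±1.5 points.

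Mean treatment difference (dupilumab minus placebo):

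| Mean number with late rescue | Week 12 outcome, Week 12 cut-off | As printed | Week 24 outcome, Week 24 cut-off | Gap at Week 24 (as printed minus Table 3) |
|---|---|---|---|---|
| 0 | -1.645 | -2.259 | -2.258 | -2.259 + 2.258 = -0.001 |
| 6.96 | -1.604 | -2.269 | -2.376 | -2.269 + 2.376 = 0.107 |
| 15.68 | -1.659 | -2.299 | -2.646 | -2.299 + 2.646 = 0.347 |
| 6.36 (region effect) | -1.704 | -2.414 | -2.481 | -2.414 + 2.481 = 0.067 |

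As printed minus the declared Week 12 endpoint: -2.259 + 1.645 = -0.614; -2.269 + 1.604 = -0.665; -2.299 + 1.659 = -0.640; -2.414 + 1.704 = -0.710.

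The standard error within a trial was about 0.4, so each scenario mean carries a simulation error of about 0.4/√25 = 0.08. Comparisons within a row use the same simulated trials and should be tighter than that, but their simulation error was not computed.

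Region coding in step 1, Week 12 estimate, numeric against categorical: -1.645 and -1.648; -1.604 and -1.604; -1.659 and -1.650; -1.704 and -1.697. The largest difference in means is 0.009. The largest gap in any single trial was 0.14, which includes imputation noise at 8 imputations.

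**The case against.** The strongest reply is that this is sample code and the prose is unambiguous. The appendix is titled as sample code, its variable lists contain an ellipsis, and it sorts the LS means by `trt01pn` although PROC GLM uses `trt01p`. It has to be adapted before it can run. Table 3 and Section 4.4.2 already fix the endpoint week and the cut-off, and changing one token brings the Week 12 block into line. All of this stands and keeps the severity low. It does not remove the contradiction: Section 5.5 says the Week 12 model will be built from this code, and Section 4.4.2 points to it for the analysis as well as the imputation.

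A reader might infer more than the documents support:

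- That the Week 12 cut-off is an error in its own right. It is correct for the declared endpoint under Section 4.4.2 and Table 3 footnote a. It conflicts with the Week 24 row only because the outcome is `chg24winrs`.
- That the numeric region code breaks Table 3. Table 3 lists region as a term in the ANCOVA and sets no rule for coding it in the imputation. Step 1 only fills intermittent gaps, and step 2 and PROC GLM treat region as categorical.
- That the supplementary hybrid responder analysis of the primary endpoint is affected. Section 4.3.4 takes the imputed Week 12 values, classifies responders and applies a CMH test. It does not use the PROC GLM line, and the Week 12 cut-off is right for it.
- That the tested Week 24 percent change is misspecified. Its rule is clear in Section 4.4.2. What is missing is a code version that matches it.

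**Conclusion.** The point holds as an internal error in the analysis specification, of low severity. The heading and cut-off in Appendix 5 say Week 12 and the modelled outcome says Week 24. Followed literally, the block estimates an endpoint other than the one declared, with a cut-off that Table 3 does not allow for the endpoint it does estimate.

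This reading needs no assumption. The sizes do: the shift of about 0.6 to 0.7 points from the declared endpoint, and the departure from Table 3 of nil to 0.35 points, depend wholly on assumed effects, spreads and late-rescue rates. They illustrate the mechanism and do not predict the trial's results. The documents also do not show that the reported Week 12 results will in fact be Week 24 results, since that requires a programmer to copy a template unaltered against clear prose. The primary CMH analysis is unaffected.

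**What to change.** Reconcile Section 5.5 before database lock:

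- Week 12 block: change the PROC GLM dependent variable to `chg12winrs`. Heading and cut-off stay as they are.
- Week 24 endpoints: add a matching version with a Week 24 heading, exclusion of events before Week 24, and the Week 24 outcome. State the outcome variable for the percent change in the hierarchies, since the printed model fits an absolute change. The hybrid supplementary analysis of the Week 24 WI-NRS responder endpoint, which Section 4.4.1.2 calls for, needs the same Week 24 cut-off.
- While editing, align `trt01p` and `trt01pn`.
- Optional, with negligible effect: replace region by 0/1 indicators in the step 1 MCMC call, to agree with step 2 and PROC GLM.

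The weekly variables need not be cut at the endpoint week, because no rule in the SAP bars later values from the imputation model. The cost is a few lines of SAP code. No estimand, hypothesis or data collection changes.
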